## 1. INTRODUCTION

Rheumatoid arthritis (RA) is associated with increased mortality from cardiovascular disease (CVD). This is thought to be due to accelerated atherosclerotic coronary heart disease (CHD), possibly occurring due to a combination of systemic inflammation augmenting an adverse cardiovascular risk profile.

Statins have a proven beneficial effect in reducing CVD events and mortality in at-risk populations, mostly due to their cholesterol-lowering properties, but also possibly through anti-inflammatory and immunomodulatory effects. Whether such benefit occurs in a high-grade inflammatory condition such as RA remains unknown, because such patients have been systematically excluded from previous statin trials.

This prospective, 5-year, multi-centre, randomised, double blind, placebo-controlled trial assesses the hypothesis that atorvastatin is more effective than placebo in the primary prevention of cardiovascular events in patients with RA\*. All patients receive lifestyle modification advice. Patients already receiving or requiring statin therapy for secondary prevention or whose managing physician thinks they should be on a statin for an existing indication will be excluded.

A nested sub-study (*TRACE RA-DAS*) investigates the hypothesis that atorvastatin is more effective than placebo as adjunctive therapy in reducing RA disease activity. Patients enrolled in *TRACE RA-DAS* have moderately or severely active disease at the time that they are recruited to the main study.

TRACE RA and TRACE RA DAS provide a unique opportunity to create a bio bank of appropriately timed DNA, RNA, plasma and serum *specimens (TRACE RA-BioBank)* that would allow assessment of important supplementary hypotheses in smaller sub-studies. These will, for example, investigate the hypothesis that environmental risk factors for RA and cardiovascular disease overlap and it is likely that there are shared genetic risk factors for the onset and progression of both conditions. A detailed analysis of the molecular markers associated with atorvastatin response in RA and in particular for investigation of inflammatory markers in RA at the level of the genome will also be possible. Whereas the creation of the bio-bank forms part of the current proposal, such sub-studies will be subject to detailed protocol formation and separate ethics approval in the future.

# 2. Background and Rationale

### 2.1 Trial Background

### 2.1.1 Cardiovascular disease mortality (CVD) and co-morbidity in RA

Rheumatoid arthritis (RA) affects about 0.8% of the adult population in the UK [1]. It is associated with significant disability and most of the efforts of the scientific community have concentrated on controlling inflammatory symptoms, minimising joint damage and improving function. It is less well appreciated that RA is associated with increased and premature cardiovascular (CV) mortality. This has not improved much over the last 3 decades, despite significant treatment advances. Almost half of all deaths in RA (and about 35-40% of the excess deaths) are due to cardiovascular disease (CVD) [2, 3].

The excess CV deaths in RA may be due to either an increased prevalence or increased case fatality of CVD in RA compared to the general population, and there is now evidence for both of these. Overall CVD (including individual risk factors such as hypertension and dyslipidaemia) is the commonest comorbidity in patients with RA [4, 5]. Although rheumatoid heart disease is common on echocardiography or autopsy it rarely causes haemodynamic upset, so is an unlikely cause of death [6]. Instead, the evidence suggests that the main cause of increased CV death in RA is ischaemic heart disease (IHD). Mortality studies show that most CV deaths in RA are due to ischaemic pathologies such as myocardial infarction (MI) or congestive heart failure (CHF); probably due to accelerated atherosclerotic coronary heart disease (CHD) [reviewed in 2, 3]. Indeed, functional and phenotypic surrogate markers for atherosclerotic CHD, such as endothelial dysfunction [7], increased carotid intima-media thickness [8, 9] and changes in arterial elasticity [10] are commoner or more pronounced in RA patients than in controls, as are serological surrogates such as coagulation abnormalities [11-14]. The outcome of acute coronary syndromes is also worse in RA than matched controls [15, 16], probably due to increased instability of atherosclerotic plaques and enhanced stress responses [17] associated with high-grade systemic inflammation characteristic of RA.

It is now accepted that atherosclerosis, like RA, is a chronic inflammatory condition [18]. Immunohistochemical studies suggest significant similarities between the mechanisms responsible for chronic synovitis and damage in the rheumatoid joint and the generation and rupture of the atherosclerotic plaque in the vasculature, including the cellular infiltrates adhesion molecule expression, cytokine millieux, free radical and degradative enzyme release [reviewed in 19-21]. This is further supported by epidemiological work in the general population showing that several serological markers of systemic inflammation may associate with cardiovascular outcomes. The best studied is CRP, the level of which, even within the normal range, is a good predictor of future MI or ischaemic stroke in the general population, whether there is pre-existing CVD or not [22, 23]. Baseline CRP is also a predictor of CVD death in patients with early inflammatory arthritis, even within 5 years from the onset of arthritis [24]. RA disease activity as assessed by the erythrocyte sedimentation rate, raised fibrinogen levels [25], joint swelling [26] or a composite score [27] has been shown to associate with CV events, CV death and overall mortality respectively.

### 2.1.2 The effect of current treatments on CVD risk and outcome in RA

Thrombotic variables may be positively or negatively affected by commonly used medications, particularly non-selective non-steroidal anti-inflammatory drugs (nsNSAIDs), cyclo-oxygenase 2 inhibitors (Coxibs) and antimalarials. The effects of other treatments for RA are less clearly defined: disease-modifying antirheumatic drugs (DMARDs) do not appear to increase overall mortality; in contrast, effective control of inflammatory activity appears to confer survival benefits [28-31]. However, it remains to be proven whether such benefits are due to improved CV outcomes, and although suppression of inflammation in RA makes good theoretical sense, we still do not know how to achieve it - and in which patients - without compromising the vasculature. For example, compared with other DMARDs, the use of methotrexate (MTX) in RA has been reported in one study to associate with reduced overall and CVD mortality in unselected patients [28], probably due to superior control of inflammation. In another study however, use of MTX in RA patients with pre-existing CVD led to a significant increase in mortality compared with other DMARDs [32]; this may be due to its anti-folate, thus potentially hyperhomocystinaemic effects [33]. Also, use of anti-TNF or potent anti-inflammatory/immunosuppressive therapy, although effective at reducing systemic inflammation, may [34] or may not [35, 36] associate with improvements in vascular function and surrogates of atherosclerosis. This emphasises the need for prospective, randomised, controlled trials to confirm any theoretical predictions.

### 2.1.3 Classical cardiovascular risk factors in RA

Inflammation in RA may affect classical CVD risk factors, including lipid metabolism. Dyslipidaemia has been well documented in RA and appears to associate with the acute phase response [37]. Most studies suggest that during active RA, total and LDL cholesterol may be reduced, but HDL is consistently found to be even further reduced leading to an unfavourable lipid profile. Control of disease activity with several drugs or use of ciclosporin may lead to elevation of all lipid levels with the lipid profile remaining unfavourable.

Generally, RA patients have a higher prevalence of vascular risk factors [38] and signs of asymptomatic arterial disease [39] than matched controls, which may be present even before the onset of inflammatory polyarthritis [40]. About a third of unselected hospital RA patients have documented CVD and/or CVD risk factors and are on treatment for these. Of the remaining two thirds, 90% have at least one modifiable risk factor. 70% and 60% have above the recommended levels of total cholesterol and systolic blood pressure respectively, and 40% have a >15% 10-year risk of a CHD event [13, 41]. Smoking, obesity and sedentary lifestyle may be important but are also more difficult to modify in RA than in the general population, due to the physical and psychosocial consequences of the disease [42]. As occurs in other high-risk groups (e.g. diabetes), pharmacological interventions targeted at hypertension and/or dyslipidaemia may be the most practical approach to this problem. Hypertension in RA may associate with the use of NSAIDs and Cox-2 inhibotors. Theoretically, ACE inhibitors (ACE-I) may have particularly beneficial effects in RA, since they have been shown to confer significant benefits in other high-risk populations [43], may have anti-oxidant properties and improve endothelial dysfunction [44]. However, other co-morbidities, polypharmacy, frequent treatment changes and the age groups characteristic of RA make both the routine use of such drugs problematic: for example, the combination of NSAIDs and ACE-I is commonly nephrotoxic, particularly in the elderly [45].

### 2.1.4 Statins

Statins have a combination of properties that makes them particularly attractive for CV outcome studies in RA: they can be delivered in single daily dosing (an important factor in patients receiving multiple medications); they do not require much monitoring over and above that usually necessary for RA patients on DMARDs, and they do not interact adversely with most of the treatments commonly used in RA.

The efficacy of statins in the primary and secondary prevention of CHD events in the 'at risk population' has been demonstrated in several trials, with a reduction of major coronary events of 35% or above [45-51]. This is related almost exclusively to their lipid-lowering effects. There is however evidence from human *in vivo* studies, animal models and *in vitro* work, which suggest that statins have several other, so called "pleiotropic" effects. These include: reduced oxidative stress, anti-inflammatory and immunomodulatory actions, improved endothelial function, beneficial effects on vascular smooth muscle cells, antithrombotic effects and even antihypertensive properties. Several of these pleiotropic effects of statins are relevant to the atherosclerotic and chronic inflammatory pathologies of RA [52-57]. This opens up the possibility that statins may be beneficial to the rheumatoid component of RA [58, 59]. Indeed, the TARA trial [60], a 'proof of principle' trial demonstrated that atorvastatin 40mg daily, as an adjunct to DMARD therapy, provided additional benefit for inflammatory control of RA in at least a subgroup of patients.

With the exception of ciclosporin (which is metabolised through cytochrome P450 and can thus increase the risk of myopathy when used with some statins) there are no known significant interactions between anti-rheumatic drugs and statins. Statins are useful for secondary and primary prevention, in patients with overt CHD or those with a 10-year CVD (CHD+stroke) risk of >20%. Recent work shows that this is the case also for low risk patients, e.g. patients with diabetes with a <15% CHD risk [61]. Whereas many statin-effects may be class effects, there is evidence to suggest individual differences. Atorvastatin appears suitable for this pragmatic study. Several studies have shown a good safety profile over a wide dose range with no need to adjust dose for renal impairment. Improvements in cardiovascular end-points have been shown in many different settings and clinical populations such as ACS, stable CHD, diabetes and hypertension, including low CV risk diabetics. Early benefits seen in some atorvastatin studies have not been seen with other statins, particularly simvastatin, whereas newer statins (e.g. rosuvastatin) currently lack a large body of endpoint data. Atorvastatin may also have better effects on plaque progression and inflammatory marker reduction than either pravastatin or simvastatin [62-68]. Atorvastatin is also the only statin that has been used in an RA population with some "proof of concept"

that, at a dose of 40mg daily, it can reduce systemic inflammation and improve lipid profile in RA [60], and has been shown to reduce arterial stiffness in patients with RA [69].

### 2.2 Rationale

### 2.2.1 Need for the trial

Cardiovascular morbidity and mortality in RA are common, severe and have not received adequate attention until very recently. No trials to date have addressed whether any intervention(s) can reduce the rate of CV events in patients with RA. Articles in leading medical journals, such as the Lancet [70] clearly identify the need for sufficiently powered and specifically designed trials addressing this problem.

The cause of the CV morbidity and mortality in RA is probably multifactorial, and may be best treated by a drug with pleiotropic effects in addition to standard lipid lowering. The proposed intervention is based on sound basic science and extensive clinical trial data in other populations. However, the efficacy and safety of such an intervention remains to be proven in the RA population which, due to its major morbidity, polypharmacy and concomitant muscle pathology has been systematically excluded from all major statin trials.

### 2.2.2 Aim of the trial

TRACE RA aims to establish whether treatment with atorvastatin will protect patients with RA aged  $\geq$ 50 years or with  $\geq$ 10 years' duration of RA from fatal and non-fatal atherosclerotic events.

A nested sub-study *(TRACE RA DAS)* has been designed to determine whether atorvastatin, used in conjunction with standard DMARD therapy, will provide added arthritis control in patients with moderately or severely active RA.

A further sub-study, (*TRACE RA BioBank*) has also been incorporated into the main study. The aim of this sub-study is as follows:

- 1. To develop a DNA, plasma and serum repository from all patients consenting to the biobank from within those enrolled in the main TRACE RA study in centres where such blood preparation is possible, and the centres agree to provide such samples.
- 2. To develop an RNA, serum and plasma repository for gene expression profiling from TRACE RA DAS subjects with sampling at baseline and at 6 months.

### 2.2.3 How the results will be used

If effective, the implementation of this intervention in the routine rheumatology clinic would be easy and, apart from the drug costs, would have no resource implications.

The trial will increase awareness of CV morbidity and mortality in RA and, in the process, identify patients who need to be properly risk-assessed and treated.

If atorvastatin also shows evidence of being a disease-modifying drug this will add to the choice of such drugs, which is at present limited. Current evidence suggests that the goal in RA treatment should be to minimise the inflammatory response – ideally aiming for remission. This is likely to slow or halt radiographic progression and to improve cardiovascular co-morbidity and mortality. All additions to the family of drugs which reduce inflammation are welcome.

## 3. Trial Design

### Trial type

Multi-centre, randomised, double blind, placebo-controlled trial

### Primary hypotheses

TRACE RA – All patients: Atorvastatin is more effective than placebo in the primary prevention of cardiovascular events in RA patients.

TRACE RA DAS patients only: Atorvastatin is more effective than placebo as adjunctive therapy for the reduction of disease activity in RA patients

### 3.1 Primary endpoints

### TRACE RA (all patients): Primary endpoints

The primary comparison will involve Cox regression analyses of "major vascular events" (defined as nonfatal myocardial infarction, non-fatal presumed ischaemic stroke, transient ischaemic attack, any coronary or non-coronary revascularisation or cardiovascular death excluding both confirmed cerebral haemorrhage [ICD I64-99 in the 10th International Classification of Diseases]) and non-coronary cardiac death [ICD I00-I15 and I26-I52] during the scheduled treatment period among all those allocated atorvastatin tablets versus all those allocated placebo tablets (i.e. "intention-to-treat" comparisons).

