## APPENDIX 5: DEFINITIONS OF CARDIOVASCULAR ENDPOINTS

An independent cardiovascular endpoint classification committee will review cardiovascular events and all deaths and will classify them according to the WHO MONICA method, or alternative of their choice.

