#### Primary Endpoints

Cardiovascular death (excluding definite haemorrhagic stroke (ICD 10: I62-67; and non-coronary cardiac death (I00- etc), non-fatal myocardial infarction, non-fatal stroke or any coronary or non-coronary revascularisation. This will comprise the following, as defined in the subsequent paragraphs:

Coronary heart disease death Fatal presumed ischaemic stroke Other atherosclerotic vascular death Myocardial infarction Myocardial infarction Nonfatal stroke Transient ischaemic attack -a mild cerebrovascular stroke with reversible symptoms that last from a few minutes to several hours Coronary revascularization Non-coronary revascularization (see below for definitions)

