# A5.1.5 Other atherosclerotic cardiovascular death (e.g. ruptured aortic aneurysm, mesenteric infarction, peripheral arterial disease):

Death certificate or equivalent documentation with consistent underlying or immediate cause and adequate preterminal documentation of the event.

*Note:* Preterminal documentation and/or information may include hospitalisation for, or diagnosis of, a vascular-related illness for a previous event other than the terminal event.

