## A5.2.4 Stroke (any event that meets the criteria listed below for one of the following 3 categories of stroke):

Ischaemic stroke (one of the following conditions must be met):

Rapid onset of focal neurological deficit lasting  $\geq$ 24 hours or leading to death plus evidence from neuroimaging (CT or MRI) showing cerebral/cerebellar infarction or no abnormality, or post-mortem examination showing cerebral and/or cerebellar infarction.

Rapid onset of global neurologic deficit (e.g. coma) lasting  $\geq$ 24 hours or leading to death plus evidence from neuroimaging showing cerebral/cerebellar infarction, or post-mortem examination showing infarction.

Focal neurologic deficit (mode of onset uncertain) lasting  $\geq$ 24 hours or leading to death plus evidence from neuroimaging showing cerebral/cerebellar infarction, or post-mortem examination showing infarction.

Primary intercerebral and/or cerebellar haemorrhage (one of the following conditions must be met):

Rapid onset of focal neurologic deficit lasting  $\geq$ 24 hours or leading to death plus evidence from neuroimaging or post-mortem examination showing primary intracerebral and/or cerebellar haemorrhage.

Rapid onset of global neurologic deficit (e.g. coma) lasting  $\geq$ 24 hours or leading to death, plus evidence from neuroimaging or post-mortem examination showing primary intracerebral and cerebellar haemorrhage.

Focal neurologic deficit (mode of onset uncertain) lasting  $\geq$ 24 hours or leading to death, plus evidence from neuroimaging or post-mortem examination showing primary intracerebral and/or cerebellar haemorrhage.

Stroke- mechanism unknown (one of the following conditions must be met):

Rapid onset of focal neurologic deficit lasting  $\geq$ 24 hours or leading to death, without neuroimaging or post-mortem data available.

Rapid onset of global neurologic deficit (e.g. coma) lasting  $\geq$ 24 hours or leading to death, without neuroimaging or post-mortem data available.

Focal neurologic deficit (mode of onset uncertain) lasting  $\geq$ 24 hours or leading to death, without neuroimaging or post-mortem data available.

*Note:* The following **conditions will be excluded** from the defined endpoint of stroke as outlined above:

Primary intracerebral haemorrhage

Primary subarachnoid haemorrhage

Subdural or extradural haematoma

Traumatic intracerebral haemorrhage

Neurologic deficit due to major metabolic or haemodynamic disturbance

Venous sinus thrombosis

Cerebral tumour

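### Section 3.1 and Appendix 5 define the primary endpoint differently: the excluded haemorrhage deaths carry two different ICD ranges, and non-fatal stroke is limited to presumed ischaemic stroke in one place but not the other

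*Protocol*

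**What the plan says.** **Deaths.** Section 3.1 includes "cardiovascular death excluding both confirmed cerebral haemorrhage [ICD I64-99 in the" (ICD-10 is then named), followed by "non-coronary cardiac death [ICD I00-I15 and I26-I52] during the scheduled treatment period". Section 3.2 repeats both code ranges for the secondary endpoint of cardiovascular death. The Primary Endpoints paragraph of Appendix 5 describes the same endpoint as "Cardiovascular death (excluding definite haemorrhagic stroke (ICD 10: I62-67; and non-coronary cardiac death (I00- etc), non-fatal myocardial infarction, non-fatal stroke". The haemorrhage range there is I62-67, and the cardiac range has no upper limit. The component list below that paragraph includes other atherosclerotic vascular death. A5.1.5 describes it as "Other atherosclerotic cardiovascular death (e.g. ruptured aortic aneurysm, mesenteric infarction, peripheral arterial disease".

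**Stroke.** Section 3.1 counts "non-fatal presumed ischaemic stroke, transient ischaemic attack, any coronary or non-coronary revascularisation". In Appendix 5, neither the summary sentence nor the component list limits non-fatal stroke to ischaemic stroke. A5.2.4 defines stroke as "any event that meets the criteria listed below for one of the following 3 categories of stroke". One of the three is "Primary intercerebral and/or cerebellar haemorrhage (one of the following conditions must be met". A note at the end of A5.2.4 takes a list of conditions back out of the stroke endpoint. Primary intracerebral haemorrhage comes first in that list; cerebellar haemorrhage is not in it.

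**The concern.** These sentences decide which events enter the primary Cox analysis (sections 3.1 and 10.4). They also decide which events count towards the number of confirmed primary events that can close the trial (section 6.4) and towards the 25%, 50% and 75% interim looks (section 10.7). If two parts of the protocol give different rules for the same death or stroke, whoever compiles the endpoint has to choose between them, and nothing in the protocol says whether section 3.1 or Appendix 5 prevails. An atorvastatin effect is expected on atherosclerotic events. Counting haemorrhages would tend to dilute it, and dropping atherosclerotic deaths would lose events on which it could be seen.

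**Working it through.** This is a comparison of definitions. The protocol gives no figure to reproduce for the size of the affected group.

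**1. The two haemorrhage ranges as sets**

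| ICD-10 headings | Section 3.1 (I64-99) | Appendix 5 (I62-67) |
|---|---|---|
| I62-I63 | not excluded | excluded |
| I64-I67 | excluded | excluded |
| I68-I99 (99 - 68 + 1 = 32 headings) | excluded | not excluded |

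**2. What section 3.1 would leave if its codes were applied literally.** Treat I00-I99 as a plain number range. Removing I00-I15 (16 headings), I26-I52 (27) and I64-I99 (36) takes out 79 of 100. That leaves I16-I25 and I53-I63, and nothing above I63. Appendix 5 cannot be worked out in the same way, because its cardiac range has no end. If one assumes the cardiac ranges of section 3.1 apply there too, it removes 16 + 27 + 6 = 49 headings and leaves I16-I25, I53-I61 and I68-I99 (51). Which codes are medically right is not judged here, because the ICD itself is not among the documents.

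**3. Non-fatal stroke, text against text**

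| Event | Section 3.1 | Appendix 5 summary | A5.2.4 categories | A5.2.4 note |
|---|---|---|---|---|
| Ischaemic stroke | in | in | in | not excluded |
| Primary intracerebral haemorrhage | out | in as worded | in | out |
| Primary cerebellar haemorrhage | out | in as worded | in | not named |

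The Appendix 5 summary refers to the definitions that follow it, so the A5.2.4 note carries upward and settles intracerebral haemorrhage. It does not settle cerebellar haemorrhage, which A5.2.4 names separately in its category.

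**4. Illustration only.** Table 1 of Appendix 8 gives 417 patients with events for a 24% reduction. Schoenfeld's formula reproduces it: 4(1.960 + 0.842)² / (ln 0.76)² = 417. Assume a share f of placebo-arm events is of a disputed type with no treatment effect, so that HR = 0.76(1 - f) + f, and power = Φ(|ln HR|·√d/2 - 1.96).

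| Assumed f | HR | Power if disputed events replace others within 417 | Power if they are added to 417 (total d) |
|---|---|---|---|
| 0 | 0.76 | 80% | 80% (417) |
| 3% | 0.767 | 77% | 79% (432) |
| 5% | 0.772 | 75% | 78% (442) |
| 10% | 0.784 | 70% | 75% (470) |

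Conversely, losing 5% of 417 events at an unchanged HR (about 396 left) gives 78%. The documents give no value of f, so none of these is an estimate for this trial.

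**The case against.** The best defence is that the intention can be read from the text. Sections 3.1 and 3.2 both say presumed ischaemic, both death definitions exclude haemorrhage, and the A5.2.4 note subtracts haemorrhage from the definition above it. The version 5 summary in Appendix 11.5 also records that haemorrhagic stroke was taken out. This largely stands, and it rules out several stronger readings:

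- A reader might infer that haemorrhagic stroke is both counted and excluded throughout. For primary intracerebral haemorrhage the A5.2.4 note states its own precedence. What remains is the unqualified wording in the Appendix 5 summary and the unnamed cerebellar haemorrhage.
- A reader might infer that haemorrhagic deaths enter through A5.1.3, which points to the stroke definition. That item is headed as presumed ischaemic, and the Appendix 5 summary excludes definite haemorrhagic stroke deaths.
- A reader might infer that section 3.1 discards the aneurysm, mesenteric and peripheral arterial deaths. That follows only if the bracketed code overrides the words it is attached to, and those words exclude only confirmed cerebral haemorrhage. The fatal criteria in A5.1 rest on documents and autopsy rather than codes, and the protocol does not map the A5.1.5 examples to ICD headings.
- A reader might see a separate defect in the statement that the committee "will classify them according to the WHO MONICA method, or alternative of their choice". That is permissive, but Appendix 5 then gives specific criteria, and the detail of adjudication usually belongs in a charter.
- A reader might fear that the endpoint will be chosen on results. Section 6.2.2 keeps patients, investigators and trial units blind, and A9.4 restricts unblinded comparative data to the DMC. A blinded clarification is not selection on results.

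The defence does not reconcile I64-99 with I62-67. These are two explicit code lists for one exclusion, and they disagree on 2 + 32 = 34 headings. Nor is this a detail left to a later analysis plan, because the protocol fixes both versions itself.

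**Conclusion.** The inconsistency is real and stands in current text. The excluded haemorrhage deaths have two code ranges that agree on only four headings. The non-coronary cardiac exclusion is closed in section 3.1 and open in Appendix 5. Non-fatal stroke is restricted in section 3.1 and unrestricted in the Appendix 5 summary, with cerebellar haemorrhage unresolved in A5.2.4. Applying one text or the other as written can therefore give different primary events.

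The effect on the result cannot be sized from the documents and is probably modest, because the adjudicated causes and the stated intention mostly point the same way. A reader might take the illustrated power losses as the expected cost. They rest on assumed shares of null-effect events with no source in the protocol, and they fall by up to five points' difference depending on whether disputed events replace true ones or add to them. The case for correction is that this is the primary endpoint and that the change is cheap, not that a loss of power has been shown.

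**What to change.** Make the change while still blinded, without sight of comparative data:

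1. Use one primary endpoint definition, in the same words, in sections 3.1 and 3.2 and in Appendix 5.
2. Define the excluded deaths by adjudicated cause: confirmed intracranial haemorrhage, and non-coronary cardiac death. Alternatively, replace both haemorrhage ranges and the open cardiac range with one checked code list that leaves the A5.1.5 deaths in.
3. Change non-fatal stroke in the Appendix 5 summary and component list to non-fatal presumed ischaemic stroke.
4. In A5.2.4, remove haemorrhage, including cerebellar, from the qualifying categories, or label it as recorded but not counted. The ischaemic and mechanism-unknown categories then remain.

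The cost is protocol wording, with matching wording in any endpoint charter. The existing endpoints committee may also need to recheck strokes and vascular deaths it has already classified.
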